## 3.4 Study grouping and methods

### 3.4.1 Study groups and interventions

The surgical method is based on the advice of the physician, mainly on the own choice of patients and the availability of equipment. After rigorous preoperative evaluation, patients who met the inclusion criteria were prepared for preoperative preparation (including preoperative antibiotics, etc.). The observation group was the SPr-breast conserving surgery group and the control group was the tradition-breast conserving surgery group.

### 3.5 Interventions

**(1) SPr-breast conserving surgery group: using single port robot.**

**(2) Tradition-breast conserving surgery group: breast surgery was**

completed with traditional surgery.

**(3) Standards for suspending or modifying the planned procedure:**

Conversion of SPr-breast conserving surgery to endoscopic or traditional breast conserving surgery is interruption due to technical difficulties or complications during intraoperative anatomical procedures that need to enable an open field conversion for further processing. Surgeons decide whether to switch to endoscopy or open for breast surgery amid concerns about patient safety, technical difficulties, inability to adequately complete robotic surgery or require treatment for related diseases.

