## Scenario summary

research topic	Application of Single-Port Robot-Assisted Breast-Conserving Surgery via Axillary Approach for Breast Cancer.
Main purpose of the study	
1. To evaluate the efficacy of single-port robots in breast cancer breast conserving surgery. Including differences in operative time and intraoperative number of lymph nodes detected.
 
2. To evaluate surgical safety: the incidence of surgical transfer and the incidence of postoperative complications.

Secondary purpose of the study	Pain and cosmetic scores of patients after breast conserving surgery under a single port robotic approach.
research design	
 Randomized controlled trial
 
 non-randomized controlled study
 
 Single-arm study
 
 Other
 
 Single-center study    multicenter study
 
Whether blind:  yes  no

subject investigated	Patients undergoing breast-conserving surgery for breast cancer.
intervention study	Single-port Robot-assisted breast-conserving surgery for breast cancer.
endpoint criteria	Success rate of breast conservation surgery under single-port robotic approach
sample capacity	Total number of cases: 100; 20 in the test group; 80 in the control group

statistical analysis	Double data entry was carried out using Excel 2010, and data analysis was performed with SPSS 25.0. The normality of continuous variables and homogeneity of variance were examined by Kolmogorov-Smirnov test and analysis of variance test respectively. For continuous variables that conformed to normal distribution and had homogeneity of variance, the independent-samples t-test was adopted. For continuous variables that did not conform to normal distribution, the Mann Whitney U test was used. For categorical variables and count data, Fisher's exact test and Pearson chi square test were employed.
Study cycle	November 2024-December 2025

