## 3. Research Design

### 3.1 Overall Study Design

-Enrollment: Subjects who meet the inclusion criteria enter the study process, including SPr-breast conserving surgery or Traditional-breast conserving surgery. The choice of the two surgical methods is based on the patients economic situation and the availability of equipment.

-Preoperative hospitalization: Collect patient disease information (including mammography, breast B ultrasound, breast enhanced MRI, etc.).

-The day of operation: Record the operation time, intraoperative bleeding volume, intraoperative complications, intraoperative adverse events, etc.

-Postoperative hospitalization: Record postoperative complications (postoperative bleeding, flap or nipple areola complex necrosis, subcutaneous emphysema, infection, capsular spasm, postoperative shoulder pain and discomfort, etc.), postoperative pain score, and postoperative pathological biopsy.

-Postoperative hospital stay: Calculated based on the number of days from surgery to discharge.

[figure not shown]
-28 days after surgery: To understand the complication rate and mortality rate within 28 days after surgery.

-90 days after surgery: To understand the complication rate and mortality rate within 90 days after surgery.

-Disease-free survival at 3 years after surgery (recurrence was defined as surgical area and distant metastasis by the time from surgery to last follow-up or date of recurrence and metastasis).

-3 year overall survival (from time from surgery to last follow-up or death).

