### 3.3.3 Exit criteria

- 1) Those who cannot complete the single-port robot breast conserving surgery and need to be converted into traditional breast conserving surgery or endoscopic breast preservation surgery.
- 2) The patient voluntarily requests to withdraw from the investigator.
- 3) The patient is associated with other non-tumor conditions so that they cannot continue to accept the study program;
- 4) After inclusion in the study, the investigator cannot be completed due to other reasons.

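### Conversion to another operation is a main safety measure, but its only definition is internally inconsistent, so the same failed robotic case may or may not be counted

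*SAP*

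**What the plan says.** The main purpose in the SAP's Scenario summary assesses surgical safety through "the incidence of surgical transfer and the incidence of postoperative complications". Conversion is not repeated among the endpoints in sections 3.8 and 4.4, and the schedule in section 3.6 has no row for it.

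Section 3.5 item (3) is the only place that says what a conversion is. It has two sentences.

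- The first defines a switch from the robot to endoscopic or conventional breast-conserving surgery as "interruption due to technical difficulties or complications during intraoperative anatomical procedures that need to enable an open field conversion".
- The second begins "Surgeons decide whether to switch to endoscopy or open for breast surgery". It then gives reasons, among them concern for the patient's safety, technical difficulty, and "inability to adequately complete robotic surgery or require treatment for related diseases".

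Three other sections bear on who is counted.

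- **Exit.** Section 3.3.3, item 1, takes out of the study patients who cannot complete the robotic operation and "need to be converted into traditional breast conserving surgery or endoscopic breast preservation surgery". No stage of the operation is given.
- **Group choice.** Section 3.1 states: "The choice of the two surgical methods is based on the patients economic situation and the availability of equipment". Section 3.4.1 adds physician advice and patient choice. Neither says at what moment the group is fixed.
- **Control group.** Section 3.5 item (2) describes controls by the conventional operation by which their surgery was finished.

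The robotic group has 20 patients in both the Scenario summary and section 4.1.

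**The concern.** For a new platform, the proportion of planned robotic operations that could not be finished as planned is the most direct measure of feasibility. It is useful only if everyone who applies the definition gets the same count. Here the two sentences of the definition differ on three things: where the operation may end, why it was changed, and at what stage. The cases on which they differ are informative ones: a switch to endoscopy, the loss of breast conservation, and a failure of access or docking.

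The denominator is also open. If converted patients exit, and the group is not fixed before surgery, a failed robotic case can disappear from the robotic group as well as from the numerator.

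**Working it through.** The plan states no conversion rate, expected or tolerated, so there is no figure to reproduce. The check sets the sections side by side and then shows the scale.

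**Step 1. Three kinds of failed robotic case against the text**

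| Case | 3.5(3), first sentence | 3.5(3), second sentence | 3.3.3 exit item 1 |
|---|---|---|---|
| Switch to endoscopic breast-conserving surgery | Listed destination, but does not meet the open-field condition | Covered | Exits the study |
| Case ends in mastectomy | Not a listed destination | Can be covered, since the open operation is not limited to conserving surgery | Not named |
| Access or docking fails, then traditional breast-conserving surgery | Doubtful; depends on whether this falls within the anatomical procedures | Can be covered as inability to complete; no stage is named | Exits the study |

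In none of the three rows do the two sentences clearly agree. The second sentence also describes who decides and why. It does not say that each such switch enters the count.

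**Step 2. The denominator**

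Sections 3.1 and 3.4.1 describe how the method is chosen, not when the group is fixed. Section 3.5 item (2) describes controls by how their operation was finished. Section 3.3.3 item 1 makes a converted patient exit. No section says that a patient planned for single-port surgery stays in that group for analysis when the operation ends otherwise.

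A related gap is section 3.3.2 item 4, which excludes patients whose margin cannot be made negative after re-resection. This is a likely route to mastectomy, although the plan does not mention mastectomy. Such a patient could leave the study as excluded.

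**Step 3. Scale**

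Input: n = 20 robotic patients (Scenario summary; section 4.1).

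- One case: 1/20 = 5 percentage points.
- Exact (Clopper-Pearson) 95% intervals for x/20:

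| Conversions counted | Rate | 95% interval |
|---|---|---|
| 0/20 | 0% | 0 to 16.8% |
| 1/20 | 5% | 0.1 to 24.9% |
| 2/20 | 10% | 1.2 to 31.7% |
| 3/20 | 15% | 3.2 to 37.9% |

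- Chance that the ambiguity affects at least one of 20 patients: 1 − (1 − p)^20, where p is the true rate of cases on which the sentences differ. The plan gives no p, so these values are assumptions: p = 2% gives 33%, 5% gives 64%, 10% gives 88%, 15% gives 96%.

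**The case against.** The strongest reply is that the two sentences belong together. Read as a whole, inability to complete the robotic operation has no stage attached, and the open operation in the second sentence is not confined to breast-conserving surgery. Early failure and mastectomy can then both be covered. The English is rough throughout, so fine exclusions should not be built on single phrases; axillary access may well be an anatomical procedure in the authors' sense. This stands. A reader might infer that the plan shuts mastectomy and early failure out of the count. The document does not support that; it leaves them unsettled.

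A reader might also infer that failed robotic cases are filed as controls. The document does not support that either. Sections 3.1 and 3.4.1 do not define the group by the operation received, and exit item 1, which names no stage, points to leaving the study. Reclassification is at most not ruled out for a case switched before robotic surgery starts. A mastectomy case is nowhere described as a control.

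Finally, failure to conserve the breast for oncological reasons differs from a failure of the platform, and keeping the two apart is a defensible choice. That is a reason to report conversions by type. It does not remove the need for a definition that says where each case belongs.

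The reply does not remove the conflict inside the first sentence between an endoscopic destination and an open field. Nor does it supply a time at which the group is fixed.

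**Conclusion.** The point holds as an ambiguity in a main safety measure. The single definition of conversion can give different counts from the same operations, and the exit rule together with the unfixed group leaves the denominator open. Each case at issue moves the rate by 5 percentage points, taking the 20 robotic patients as the denominator. One such case moves the upper 95% limit from 16.8% to 24.9%.

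It cannot be said that the reported rate will be too low, or by how much. The plan gives no conversion rate, and the number of affected cases is unknown. What can be said is that the rate will depend on which sentence is applied, and that the cases in doubt are all failures to complete the planned operation.

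**What to change.** Reconcile sections 3.3.3 item 1, 3.5 item (2) and 3.5 item (3) for analysis purposes, with one counting rule:

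- **Group.** Fix each patient's analysis group at the preoperative decision for single-port surgery, and keep it whatever operation follows.
- **Event.** Count as a conversion every patient planned for single-port surgery and brought to the operating room whose operation was not completed as single-port breast-conserving surgery, whatever the stage, the reason or the final operation.
- **Reporting.** Give the total and the breakdown by type (endoscopic, open breast-conserving, mastectomy). The denominator is all patients planned for single-port surgery and brought to the operating room, with an exact 95% interval.

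This changes only how cases are counted. The surgeon's decision to switch stays as the plan has it.

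The cost is a rewording of these sections and one case report form item recording planned and completed operation. The reported conversion rate may be higher than under a narrow reading of the present text.

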**3.6 Study process**

Experimental procedure	Enrollment-P reoperative	On the day of the operation	Postoperati ve hospital stay	follow-up period				
				28d	3m	6m	1y	3y
Basic data								
Informed consent	√							
Demographic data	√							
A history of tumor-related	√							
Check-up	√							
Vital sign	√							
Disease data								
Tumor stage	√		√					
Tumor molecular typing	√		√					
Immunohistochemistry of tumors	√		√					
Preoperative puncture	√		√					

biopsy								
laboratory examination								
Routine urine test	√							
Routine blood test	√			√	√	√	√	√
Blood biochemical	√			√	√	√	√	√
Coagulation function	√							
Electrocardiogram	√							
Echocardiogram	√							
Hepatitis B etiology caused by scientific examination	√							
Liver and kidney work	√			√	√	√	√	√
Blood fat	√			√	√	√	√	√
Color ultrasound (axillary lymph nodes, supraclavicular lymph nodes, breast)	√					√	√	√
Breast molybdenum target	√					√	√	√
Mammary gland MRI	√					√	√	√
Tumor marker								
CA-153	√			√	√	√	√	√
CA-199	√			√	√	√	√	√
CEA	√			√	√	√	√	√
Surgery-related indicators								
Operation time		√						
Intraoperative bleeding		√						
Dwelling time of the			√	√	√	√	√	√

drainage tube								
Length of stay			√	√	√	√	√	√
Post-operative pain score			√					
Postoperative beauty score				√	√	√	√	√

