### 3.8 Endpoint evaluation index

To verify the safety and efficacy of the single-port robot (SPr) in breast conserving surgery, the primary endpoint of this study was the success rate of breast conserving surgery. Successful breast-conserving surgery was determined by a negative tumor margin at least 2-3mm from normal tissue, and secondary endpoints included postoperative pain score and cosmetic score.

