#### 3.8.2 Secondary endpoint indicators

Measurement of postoperative pain score and postoperative cosmetic score according to the scale (measured time after patient discharge).

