#### 4.3 Preliminary analysis

Two-person data entry was performed using Excel 2010 and SPSS 25.0 data analysis. Baseline numerical data will be described as mean, standard deviation or median and interquartile range, and baseline categorical data will be shown as percentage. Normality and homogeneity of variance of continuous variables were tested by Kolmogorov-Smirnov test and ANA variance, respectively. Independent sample t-test for continuous variables meeting normal distribution and homogeneity of variance, Mann Whitney U test for continuous variables not meeting normal distribution, and Fishers exact test and Pearson chi square test for categorical variables and count data. Primary endpoint analysis: The success rate of breast conservation surgery under single hole robot will be compared by Chi-square test (Chi-square test) with exact test if necessary. Use multiple interpolation methods to deal with missing data. Postoperative cosmetic score and postoperative pain score were calculated and analyzed according to the standard scale.

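### The cosmetic score is planned only after surgery and compared without adjustment in self-selected groups, so any preoperative difference in breast appearance or satisfaction would enter the estimated effect.

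*SAP*

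**What the plan says.** SAP 3.8 names the endpoint: "secondary endpoints included postoperative pain score and cosmetic score". Section 3.8.2 sets the timing: "Measurement of postoperative pain score and postoperative cosmetic score according to the scale (measured time after patient discharge". The schedule in 3.6 agrees. The row "Postoperative beauty score" is ticked at 28 days, 3 months, 6 months, 1 year and 3 years, and is empty in the enrolment-preoperative column.

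Two sections describe how patients reach a group. Section 3.1: "The choice of the two surgical methods is based on the patients economic situation and the availability of equipment". Section 3.4.1: "The surgical method is based on the advice of the physician, mainly on the own choice of patients and the availability of equipment". The scenario summary marks the study as non-randomised and not blinded.

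For the analysis, 4.3 has: "Independent sample t-test for continuous variables meeting normal distribution and homogeneity of variance, Mann Whitney U test for continuous variables not meeting normal distribution". On this endpoint it adds only: "Postoperative cosmetic score and postoperative pain score were calculated and analyzed according to the standard scale". The scale is not named. No covariate adjustment, change score, matching or propensity method appears.

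**The concern.** Under randomisation, a comparison of postoperative scores alone is unbiased, and a preoperative value only improves precision. Here patients and physicians choose the operation, partly according to means. Patients who take the robotic operation may differ beforehand in breast shape, symmetry or satisfaction with the breast. Nothing in the design records such a difference for this score, and nothing in the analysis removes it, so it would be read as an effect of the technique.

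Cosmetic outcome is one of the benefits on which the SAP's background section rests its case for the technique. A biased comparison weakens the evidence for that benefit. A preoperative rating that is not taken before the operation cannot be obtained afterwards.

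**Working it through.** **Figures in the SAP.** The SAP gives no SD, effect size, alpha or power for the cosmetic score, so there is no figure to reproduce. The sizes below are illustrations. The group sizes are from the SAP: 20 vs 80 in the scenario summary, 20 vs 60 in 4.1. The values of r and d, the two-sided 5% level and equal SDs are assumptions.

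**Bias.** Let d be the preoperative group difference in SD units and r the within-group correlation of preoperative with postoperative score. With a linear relation and no true effect of the operation, the expected postoperative difference is

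bias = r × d.

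**Chance of a significant result with no true effect.** By normal approximation, with SE = √(1/20 + 1/n) in SD units:

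rate = Φ(rd/SE − 1.96) + Φ(−rd/SE − 1.96).

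- For n = 80, SE = √(0.05 + 0.0125) = 0.25.
- For n = 60, SE = √(0.05 + 0.0167) = 0.258.

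Worked case, r = 0.5, d = 0.5, n = 80: bias = 0.25, and 0.25/0.25 = 1. The rate is Φ(−0.96) + Φ(−2.96) = about 17%.

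| d | r | Bias (SD) | Rate, 20 vs 80 | Rate, 20 vs 60 |
|---|---|---|---|---|
| 0.2 | 0.3 | 0.06 | 5.7% | 5.6% |
| 0.2 | 0.5 | 0.10 | 6.9% | 6.7% |
| 0.2 | 0.7 | 0.14 | 8.7% | 8.4% |
| 0.5 | 0.3 | 0.15 | 9.2% | 8.9% |
| 0.5 | 0.5 | 0.25 | 17.0% | 16.2% |
| 0.5 | 0.7 | 0.35 | 28.8% | 27.3% |
| 0.8 | 0.3 | 0.24 | 16.0% | 15.3% |
| 0.8 | 0.5 | 0.40 | 36.0% | 34.1% |
| 0.8 | 0.7 | 0.56 | 61.0% | 58.3% |

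The nominal rate is 5%. The range runs from negligible to severe, and the SAP does not show where the study lies in it.

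**Precision.** Adjusting for the preoperative score multiplies the variance by 1 − r² if the groups are balanced on it. Imbalance costs part of that gain. With d = 0.5 and 20 vs 80, the variance is inflated by a factor of about 1 + (d²/98)/(1/20 + 1/80) = 1 + 0.00255/0.0625 = 1.04. The net SE ratio is √((1 − r²) × 1.04):

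- r = 0.3: about 0.97, an SE about 3% smaller
- r = 0.5: about 0.88, about 12% smaller
- r = 0.7: about 0.73, about 27% smaller

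**The case against.** The strongest objection is that the scale is unknown. A preoperative score is informative only if the scale rates something that is present before surgery. The SAP's discussion of appearance leans on scars: inclusion criterion 1 asks for a chest without one, and criterion 2 excludes earlier chest surgery and radiotherapy. A score made up of scar items would barely vary before the operation. Then r would be near zero, and so would the bias and the precision gain described above. This stands, and it makes the point conditional on the scale.

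Four stronger readings are tempting, and the SAP does not support them.

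- A reader might infer that without this baseline no adjustment can help. But demographics, tumour stage, mammography, ultrasound and MRI are collected before surgery, so partial adjustment is possible.
- A reader might infer the converse, that a baseline score would make the groups comparable. It would not: finances, expectation and unblinded rating would remain.
- A reader might take the preoperative score to be the most predictive covariate, or cosmesis to be the main claimed advantage. The SAP shows neither. Its stated main purposes are operative time, lymph nodes, conversion and complications, and cosmesis is secondary.
- A reader might argue that recruiting patients with high cosmetic demands creates the group difference. That criterion applies to both groups and, like the criterion on breast volume, may narrow the difference. The route for bias is the choice of operation. Finances and equipment availability are not shown to relate to breast appearance; patient choice, in 3.4.1, is the more plausible link.

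**Conclusion.** The point holds in a limited form. The SAP plans the cosmetic score only after surgery, lets the operation be chosen, and compares the groups without adjustment. A preoperative difference in shape, symmetry or satisfaction would therefore pass into the estimated effect, attenuated by the factor r. The SAP does not show that such a difference exists, and the size rests wholly on assumed r and d. The conclusion does not depend on whether there are 60 or 80 controls. It concerns a secondary endpoint and leaves the primary comparison of success rates untouched. It is a worthwhile, inexpensive improvement, provided the scale includes items that can be rated before surgery.

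**What to change.** - **Scale (3.8.2, 4.3):** name the cosmetic scale and state which of its items exist before surgery (shape, symmetry, satisfaction) and which do not (scar).
- **Schedule (3.6):** add a rating of the preoperative items in the enrolment-preoperative column, by the same type of rater as after surgery.
- **Analysis (4.3):** replace the unadjusted test of the cosmetic score by a linear regression on group and preoperative score, with prespecified prognostic covariates already collected, such as age, tumour stage and imaging-based size. Report the adjusted difference with its 95% interval.
- **Limits:** state that this removes only the part of the selection bias carried by the measured covariates, and list finances, expectation and unblinded rating as remaining limitations.
- **If the scale has only scar-type items:** the preoperative rating adds little, and the adjustment should rest on the covariates already collected.

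The cost is one short rating at an existing visit and a few lines of SAP text. Patients operated on before the change will have no preoperative value. Section 10 places screening and enrolment between November 2024 and June 2025, so a late change could leave a material share of the 20 robotic patients without one.
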